Appendix 10. Work Productivity and Activity Impairment Questionnaire: Low Back Pain (WPAI:LBP)

The following questions ask about the effect of your **LOW BACK PAIN** on your ability to work and perform regular activities. *Please fill in the blanks or circle a number, as indicated.*

1. Are you currently employed (working for pay)? _____ NO ___ YES
If NO, check "NO" and skip to question 6.

The next questions are about the **past seven days**, not including today.

2. During the past seven days, how many hours did you miss from work because of problems associated with your **LOW BACK PAIN**? *Include hours you missed on sick days, times you went in late, left early, etc., because of your LOW BACK PAIN. Do not include time you missed to participate in this study.*

_____ HOURS

3. During the past seven days, how many hours did you miss from work because of any other reason, such as vacation, holidays, time off to participate in this study?

_____ HOURS

4. During the past seven days, how many hours did you actually work?

_____ HOURS *(If "0", skip to question 6).*

5. During the past seven days, how much did your **LOW BACK PAIN** affect your productivity while you were working?

Think about days you were limited in the amount or kind of work you could do, days you accomplished less than you would like, or days you could not do your work as carefully as usual. If LOW BACK PAIN affected your work only a little, choose a low number. Choose a high number if LOW BACK PAIN affected your work a great deal.

Consider only how much **LOW BACK PAIN** affected productivity while you were working.

LOW BACK PAIN had no effect on my work												LOW BACK PAIN completely prevented me from working
	0	1	2	3	4	5	6	7	8	9	10	

CROSS A NUMBER

6. During the past seven days, how much did your **LOW BACK PAIN** affect your ability to do your regular daily activities, other than work at a job?

By regular activities, we mean the usual activities you do, such as work around the house, shopping, childcare, exercising, studying, etc. Think about times you were limited in the amount or kind of activities you could do and times you accomplished less than you would like. If LOW BACK PAIN affected your activities only a little, choose a low number. Choose a high number if LOW BACK PAIN affected your activities a great deal.

Consider only how much LOW BACK PAIN affected your ability to do your regular daily activities, other than work at a job.

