Appendix 17. Treatment Satisfaction Questionnaire for Medication v.II

TREATMENT SATISFACTION QUESTIONNAIRE FOR MEDICATION - VERSION II TSQM:

Instructions: Please take some time to think about your level of satisfaction or dissatisfaction with the medication you are taking in this clinical trial. We are interested in your evaluation of the effectiveness, side effects, and convenience of the medication over the last two to three weeks, or since you last used it. For each question, please place a single check mark next to the response that most closely corresponds to your own experiences.

1. How satisfied or dissatisfied are you with the ability of the medication to prevent or treat your condition?

- (1) Extremely Dissatisfied
- (2) Very Dissatisfied
- (3) Dissatisfied
- (4) Somewhat Satisfied
- (5) Satisfied
- (6) Very Satisfied
- (7) Extremely Satisfied

2. How satisfied or dissatisfied are you with the way the medication relieves symptoms?

- (1) Extremely Dissatisfied
- (2) Very Dissatisfied
- (3) Dissatisfied
- (4) Somewhat Satisfied
- (5) Satisfied
- (6) Very Satisfied
- (7) Extremely Satisfied

3. As a result of taking this medication, do you experience any side effects at all?

- (1) Yes
- (0) No

4. How dissatisfied are you by side effects that interfere with your physical health and ability to function (e.g., strength, energy levels)?

- (1) Extremely Dissatisfied
- (2) Very Dissatisfied
- (3) Somewhat Dissatisfied
- (4) Slightly Dissatisfied
- (5) Not at all Dissatisfied

TREATMENT SATISFACTION QUESTIONNAIRE FOR MEDICATION - VERSION II TSQM:

5. How dissatisfied are you by side effects that interfere with your mental function (e.g., ability to think clearly, stay awake)?

- (1) Extremely Dissatisfied
- (2) Very Dissatisfied
- (3) Somewhat Dissatisfied
- (4) Slightly Dissatisfied
- (5) Not at all Dissatisfied

6. How dissatisfied are you by side effects that interfere with your mood or emotions (e.g., anxiety/fear, sadness, irritation/anger)?

- (1) Extremely Dissatisfied
- (2) Very Dissatisfied
- (3) Somewhat Dissatisfied
- (4) Slightly Dissatisfied
- (5) Not at all Dissatisfied

7. How satisfied or dissatisfied are you with how easy the medication is to use?

- (1) Extremely Dissatisfied
- (2) Very Dissatisfied
- (3) Dissatisfied
- (4) Somewhat Satisfied
- (5) Satisfied
- (6) Very Satisfied
- (7) Extremely Satisfied

8. How satisfied or dissatisfied are you with how easy it is to plan when you will use the medication each time?

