6.2.7. Work Productivity and Activity Impairment Questionnaire: Low Back Pain (WPAI:LBP)

WPAI:LBP change from Baseline to Week 16, 56 and 64, in the percent work time missed due to chronic low back pain, percent impairment while working due to chronic low back pain, percent overall work impairment due to chronic low back pain, and percent activity impairment due to chronic low back pain.

This summary of WPAI:LBP will use observed data only (no imputation for missing data). These are listed below:

- Percent work time missed due to Low Back Pain.
- Percent impairment while working due to Low Back Pain.
- Percent overall work impairment due to Low Back Pain.
- Percent activity impairment due to Low Back Pain.

The calculation of these endpoints is described in [Appendix 2.3](#). The change from Baseline in the impairment scores of the WPAI:LBP will be summarized by treatment group.

The summary will show number and percentage of patients with a decrease, no change, and an increase in score for the change from Baseline to each timepoint. In addition, descriptive statistics (mean, standard deviation, median, min, max, number of subjects) for the change from Baseline to each timepoint and the absolute scores at the individual timepoints of Baseline and Weeks 16, 56, and 64 will be calculated.

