6.2.11. Treatment Satisfaction Questionnaire for Medication v.II (TSQM) Score

TSQM score at Weeks 16 and 56.

The Weeks 16 and 56 responses in the 4 TSQM parameters of satisfaction with effectiveness, side effects and convenience, and overall satisfaction will be summarized.

Summary tables showing number and percentage of patients by value and treatment group will be shown for TSQM items 1-2 and 4-11, and the four satisfaction parameters.

This summary and analysis will use observed data only (no imputation for missing data). The calculation of these endpoints are described in [Appendix 2.3](#).

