Appendix 2.3. Further Definition of Endpoints

Health State Utility of the EQ-5D-5L

The EQ-5D-5L contains five questions that measure the following dimensions: mobility, self-care, usual activities, pain/discomfort, and anxiety/depression. Each of the five dimensions has five levels: (1) no problems; (2), slight problems; (3) moderate problems; (4) severe problems; and (5) extreme problems.

The health utility scores are defined for every possible set of outcome combinations of the five dimensions for the following countries:

- Denmark, France, Germany, Japan, the Netherlands, Spain, Thailand, UK, US and Zimbabwe.

It is intended that this study will recruit patients from Japan.

WPAI:LBP Endpoints

The tables below summarizes the 6 questions of the WPAI:LBP questionnaire, and the four endpoints of the effect of impairment on activity and impairment.

| Question | Question Wording | Scoring |
|----------|---|---|
| 1 | Are you currently employed? [if No skip to question 6] | Yes, No |
| 2 | During the past seven days, how many hours did you miss from work due to problems associated with your Low Back Pain | number of hours (free text) |
| 3 | During the past seven days, how many hours did you miss from work because of any other reason, such as vacation, holidays, time off to participate in this study? | number of hours (free text) |
| 4 | During the past seven days, how many hours did you actually work (if '0' skip to Question 6) | number of hours (free text) |
| 5 | During the past seven days, how much did your Low Back Pain affect productivity while you were working? | 0 to 10 scale with 0 being 'Low Back Pain had no effect on my work' and 10 being 'Low Back Pain completely prevented me from working' |
| 6 | During the past seven days, how much did your Low Back Pain affect your ability to do your regular daily activities, other than work at a job? | 0 to 10 scale with 0 being 'Low Back Pain had no effect on my daily activities' and 10 being 'Low Back Pain completely prevented me from doing my daily activities' |

| | |
|---|--|
| WPAI endpoint | Calculation |
| Percent activity impairment due to Low Back Pain | $Q6*10$ |
| Percent impairment while working due to Low Back Pain | $Q5*10$ |
| Percent overall work impairment due to Low Back Pain | $\left\{ \frac{Q2}{Q2+Q4} + \left[1 - \left(\frac{Q2}{Q2+Q4} \right) \right] \left(\frac{Q5}{10} \right) \right\} \times 100$ |
| Percent work time missed due to Low Back Pain | $\frac{Q2}{Q2+Q4} * 100$ |

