TSQM vII

The 11 questions of the TSQM and the scoring are shown below:

| Item | Question wording | Likert Scoring |
|------|---|---|
| 1 | How satisfied or dissatisfied are you with the ability of the medication to prevent or treat the condition? | 1 (Extremely dissatisfied) to 7 (Extremely satisfied) |
| 2 | How satisfied or dissatisfied are you with the way the medication relieves symptoms? | 1 (Extremely dissatisfied) to 7 (Extremely satisfied) |
| 3 | As a result of taking this medication, do you experience any side effects at all? | 0 (No), 1 (Yes) |
| 4 | How dissatisfied are you by side effects that interfere with your physical health and ability to function (eg, strength, energy levels)? | 1 (Extremely dissatisfied) to 5 (Not at all dissatisfied) |
| 5 | How dissatisfied are you by side effects that interfere with your mental function (eg, ability to think clearly, stay awake)? | 1 (Extremely dissatisfied) to 5 (Not at all dissatisfied) |
| 6 | How dissatisfied are you by side effects that interfere with your mood or emotions and ability to function (eg, anxiety/fear, sadness, irritation/anger)? | 1 (Extremely dissatisfied) to 5 (Not at all dissatisfied) |
| 7 | How satisfied or dissatisfied are you with how easy the medication is to use? | 1 (Extremely dissatisfied) to 7 (Extremely satisfied) |
| 8 | How satisfied or dissatisfied are you with how easy it is to plan when you will use the medication each time? | 1 (Extremely dissatisfied) to 7 (Extremely satisfied) |
| 9 | How satisfied or dissatisfied are you by how often you are expected to use/take the medication? | 1 (Extremely dissatisfied) to 7 (Extremely satisfied) |
| 10 | How satisfied are you that the good things about this medication outweigh the bad things? | 1 (Extremely dissatisfied) to 7 (Extremely satisfied) |
| 11 | Taking all things into account, how satisfied or dissatisfied are you with this medication? | 1 (Extremely dissatisfied) to 7 (Extremely satisfied) |

The scoring of the 4 satisfaction parameters are shown in the table below.

| TSQM Parameter | Scoring |
|---------------------|--|
| Effectiveness | $[(\text{Item 1} + \text{Item 2}) - 2] / 12 * 100$ |
| Side Effects | $[(\text{Item 4} + \text{Item 5} + \text{Item 6}) - 3] / 12 * 100$ If one item is missing then: $[(\text{Sum of two completed items}) - 2] / 8 * 100$ |

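### WPAI:LBP overall work impairment has no scoring rule for an employed subject who worked zero hours, so a full week lost to back pain is computed as missing instead of 100%

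*SAP*

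**What the plan says.** SAP Appendix 2.3 lists the six WPAI:LBP questions and defines four endpoints from them. For Q4 the table reads "During the past seven days, how many hours did you actually work (if '0' skip to Question 6". The form that subjects complete, in Protocol Appendix 10, has the same instruction at Q4: "If '0', skip to question 6". Both documents therefore route anyone with zero hours worked past Q5.

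The four endpoints are:

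- activity impairment, from Q6 alone;
- impairment while working, from Q5 alone;
- work time missed, from Q2 and Q4;
- overall work impairment, from Q2, Q4 and Q5.

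Appendix 2.3 gives no rule for Q4=0. SAP 6.2.7 states: "This summary of WPAI:LBP will use observed data only (no imputation for missing data". That section then summarises the scores at Baseline and Weeks 16, 56 and 64, the change from Baseline, and the counts of subjects whose score fell, stayed the same or rose.

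**The concern.** The skip, the formula and the observed-data rule are each reasonable alone. Together they create a missing value by design for the subjects with the worst possible work outcome. The blank does not come from a visit not made or a form left unfinished. The questionnaire produces it because the subject was too impaired to work at all.

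Three consequences follow.

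- The mean of overall work impairment omits its highest values.
- The change-from-Baseline summary loses the same people. Someone off work all week at Baseline who is working at Week 56 is potentially a large improver, and someone who moves the other way is a large worsening. Neither would have a change score.
- The two work endpoints stop being comparable. For any one subject overall impairment cannot be below work time missed, but the reported means could show that order because they rest on different subjects.

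**Working it through.** **Inputs.** The formulas and the skip are from SAP Appendix 2.3, the printed skip is from Protocol Appendix 10, and the missing-data rule is from SAP 6.2.7. The plan states no numerical result for this endpoint, so there is no figure of its own to reproduce.

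**Formulas.** Let m = Q2/(Q2+Q4).

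- Work time missed = 100 × m
- Impairment while working = 10 × Q5
- Overall impairment = 100 × [m + (1 − m) × Q5/10]

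**Ordinary case** (Q2=8, Q4=32, Q5=5). m = 8/40 = 0.20. Time missed = 20%, impairment while working = 50%, overall = 100 × (0.20 + 0.80 × 0.5) = 60%. The formulas work as intended.

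**Whole week lost to back pain** (Q2=40, Q4=0, Q5 skipped). m = 40/40 = 1.

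- Time missed = 100%.
- Impairment while working has no value. That is correct, because the subject did not work.
- Overall = 100 × [1 + (1 − 1) × missing/10]. Evaluated directly, zero times missing is missing, so the score is missing.
- With any value of Q5 put in (0, 5 or 10), the result is 100 × [1 + 0] = 100%. The answer is fixed without Q5.

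**No hours worked and none missed for back pain** (Q2=0, Q4=0, for example a vacation week). m = 0/0, so time missed and overall impairment are both undefined. Here no value is implied, and missing is the sensible result, but the SAP does not say so.

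**Ordering of the two endpoints.** Overall minus time missed = 100 × (1 − m) × Q5/10, which is never negative for one subject. Means can break this order only when the contributing subjects differ, as they do here.

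**Size for one subject.** Suppose n employed subjects in an arm, one of them off all week, and the others averaging 35%. The mean without that subject is 35. With that subject at 100 it is 35 + (100 − 35)/n.

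| n employed (assumed) | Shift in arm mean |
|---|---|
| 50 | 65/50 = 1.3 points |
| 30 | 65/30 = 2.2 points |

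**Size by frequency.** If a fraction f of employed subjects is off all week and the others average μ, the shift is f × (100 − μ). At f = 2% and μ = 50 it is 1.0 point. At f = 10% and μ = 30 it is 7.0 points. All of n, f, μ and the 35% are assumptions, because the documents give none of them.

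**The case against.** The best defence is that the formula is not wrong. The weight on Q5 is exactly zero in this case, and a programmer who sees that will return 100. The subject also stays in the WPAI results through work time missed and activity impairment. The situation needs someone who is employed, worked no hours in the past seven days and missed hours because of back pain. Exclusion criterion 7, which removes current or pending compensation and disability claims, may make that uncommon. The SAP shows the number of subjects beside each summary, so a careful reader could notice the smaller denominator. No hypothesis is tested (SAP 5.1).

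Most of this stands, and it limits the point to an unspecified case with small effect. It does not remove the point. The result depends on an unstated programming choice, and the literal reading under an observed-data rule gives the wrong one. The SAP fills such gaps elsewhere: the autonomic survey impact score takes 0 where a symptom is absent (3.5.4), and unselected health-care items are scored 0 (Appendix 2.3).

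A reader might infer that the omission biases the comparison between arms. The documents give no frequency by arm, so neither a difference nor its direction is supported.

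A reader might also infer a parallel fault in the TSQM Side Effects score, namely that subjects with no side effects lose their score. The documents do not support that. No skip is printed after item 3, either in Protocol Appendix 17 or in the SAP table. Items 4 to 6 offer a top category that such a subject can tick: 5, 5, 5 gives (15 − 3)/12 × 100 = 100. With one item blank, (10 − 2)/8 × 100 = 100. The score is missing only if two or three of those items are blank, and nothing says that this happens. Setting the score to 100 whenever item 3 is answered No would also overwrite recorded answers.

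**Conclusion.** The WPAI:LBP point holds. As written, the SAP computes overall work impairment as missing for an employed subject who lost the whole week to back pain, although the formula allows only 100%. The same subject counts as 100% on work time missed, so the two endpoints rest on different subjects and the worst outcomes drop out of one of them and out of its change-from-Baseline summary.

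The impact is small: one of four WPAI scores, secondary and descriptive, with about 1.3 to 2.2 points on an arm mean per affected worker under the assumptions shown. No conclusion of the trial depends on it.

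A separate and minor observation concerns TSQM item 3, which asks "As a result of taking this medication, do you experience any side effects at all". SAP 6.2.11 says that tables "will be shown for TSQM items 1-2 and 4-11, and the four satisfaction parameters", which leaves item 3 out, while Protocol 9.3 commits to summarising all TSQM data. The SAP is allowed to modify the protocol, and adverse-event tables cover tolerability, so this is a loose end and not a safety gap.

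**What to change.** Add to the WPAI:LBP table in SAP Appendix 2.3, for every visit including Baseline: if Q2>0 and Q4=0, percent overall work impairment is 100; if Q2=0 and Q4=0, percent work time missed and percent overall work impairment are both missing. Leave impairment while working missing whenever Q4=0. Subjects with no hours worked are then handled alike in work time missed and overall impairment.

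Optionally, include TSQM item 3 in the 6.2.11 item table, by arm and visit, to match Protocol 9.3. Leave the TSQM Side Effects scoring as it is.

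The cost is one sentence in the SAP, one condition in the derivation program and, if wanted, one table row. No new data are needed.

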6.2.9. Usage of Rescue Medication

Usage of rescue medication (incidence, and number of days of usage) during Weeks 1, 2, 4, 8, 12, 16, 24, 32, 40, 48, 56 and 64.

Incidence of rescue medication use will be summarized up to Week 64 using observed data and LOCF imputation. Imputation of weekly diary data after week 56 will not be performed. Number and percentage of subjects taking rescue medication will be shown.

The rescue medication data will be converted to Weekly scores for the week prior to the timepoint of interest. Calculation of the endpoints for both the IPAP and the concomitant medication log data collection is described in [Appendix 2.3](#).

The number of days of rescue medication use per week endpoint will be summarized for the Weeks 1, 2, 4, 8, 12, 16, 24, 32, 40, 48, 56 and 64 using observed data and LOCF imputation. Imputation of weekly diary data after week 56 will not be performed. For this analysis, Baseline data will not be carried forward in the case of a post-Baseline observation not being available for use in LOCF. Number of subjects, mean, median, standard deviation, minimum and maximum will be shown.

Usage of rescue medication (amount taken) during Weeks 1, 2, 4, 8, 12, and 16.

The amount of rescue medication use per week will be summarized for the Weeks 1, 2, 4, 8, 12 and 16 using observed data and LOCF imputation. For this analysis, Baseline data will not be carried forward in the case of a post-Baseline observation not being available for use in LOCF. Number of subjects, mean, median, standard deviation, minimum and maximum will be shown.

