| 12 | 78-84 |
| 13 | 85-91 |
| 14 | 92-98 |
| 15 | 99-105 |
| 16 | 106-112 |

At the Screening visit only, the Low Back Pain Intensity (Numeric Rating Scale) will be administered with a patient worksheet for screening purposes. Also, the daily LBPI scores collected during the Initial Pain Assessment Period (Days-5 to -1), will be averaged to assess versus study inclusion criteria.

However, if a subject receives the Week 16 injection dose prior to Day 113, the Week 16 score will be calculated using the mean of the available scores from the 7 calendar days immediately prior to the Week 16 injection dose date. Any scores used in this calculation of Week 16 will not also be used in an earlier week calculation, eg, if the Week 16 dose occurs on Day 109, the available scores from Days 102-108 will be used to calculate the Week 16 score, and the available scores from Days 99-101 will be used to calculate the Week 15 score.

After the Week 16 visit, these are grouped in 4-week intervals using visit windows as shown below. If a subject comes in late for a Week 16 visit (or weekly diary is not activated at the visit), and so has daily diary data collected past Day 112, these data will be averaged with any data obtained weekly for any given interval.

All available on- or off-treatment data will be used for these windows after the planned treatment period.

| Summary Week | Includes Weeks | Days |
|--------------|----------------|---------|
| 20 | 17 - 20 | 113-140 |
| 24 | 21 - 24 | 141-168 |
| 28 | 25 - 28 | 169-196 |
| 32 | 29 - 32 | 197-224 |
| 36 | 33 - 36 | 225-252 |
| 40 | 37-40 | 253-280 |
| 44 | 41-44 | 281-308 |
| 48 | 45-48 | 309-336 |
| 52 | 49-52 | 337-364 |
| 56 | 53-56 | 365-392 |
| 60 | 57-60 | 393-420 |
| 64 | 61-64 | 421-448 |

When multiple observations occur in a day for pain score collected weekly, the average of scores will be used.

For rescue medication, data are collected until the end of study (Week 80 or final ET). Additional windows are defined below

| Summary Week | Includes Weeks | Days |
|--------------|----------------|---------|
| 68 | 65 - 68 | 449-476 |
| 72 | 69 - 72 | 477-504 |
| 76 | 73 - 76 | 505-532 |
| 80 | 77 - 80 | 533-560 |

Besides the windows specified above, there is one additional window as defined as follows:

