Rescue medication data is collected daily using an electronic system up to Week 16, and weekly after Week 16 and up to Week 64. Daily and Weekly collected data will be assigned to a specific study week for summary and reporting. The assignment of daily and weekly data to weeks will use the same principle as described above in [Appendix 2.1](#) for the weekly aLBPI data.

The incidence of rescue medication use will look for any incidence in the week of interest (collected through daily or weekly diary data). The number of days of RM use (using daily and weekly data) and the total amount taken (using daily data up to Week 16 only) over the week will be calculated for the assigned week algorithm described above.

Imputation is described in [Section 5.3](#) above. Imputation occurs for daily data up to Week 16 where the patient is in the trial and up to the end of that particular week.

An example of imputation and calculating the three endpoints using the daily diary data is shown below.

Example of calculating rescue medication data from Daily Diary Data (Patient does not discontinue)

In this example, a patient has a Week 2 visit on study day 14 (slightly earlier than the nominal day 15). Study days 8-14 would represent Week 2 data.

Using the Week 2 interval described above for a subject, ie, study days [8-14], we have the following rescue medication example data.

The amount taken and number of days of rescue medication use is adjusted for the duration of the Weekly interval.

| Study Day (Week) | Number of Doses of RM taken [1] | Number of Doses of RM taken [1] with LOCF imputation |
|------------------|---------------------------------|--|
| 8 (Week 2) | 2 | 2 |
| 9 (Week 2) | Missing | 2 [2] |
| 10 (Week 2) | 0 | 0 |
| 11 (Week 2) | 1 | 1 |
| 12 (Week 2) | Missing | 1 [2] |
| 13 (Week 2) | 2 | 2 |
| 14 (Week 2) | 0 | 0 |

[1] 500mg tablets of acetaminophen; [2] Using LOCF imputation for missing data

For this subject the following data will be calculated for Week 2:

- Incidence of rescue medication taken in Week 2: Yes. Rescue medication taken on days 8, 9 (imputed), 11, 12 (imputed), 13.
- Number of days of rescue medication use in Week 2: 5. For days 8-14 we have rescue medication taken on days 8, 9 (imputed), 11, 12 (imputed), and 13. The number of days taken for the 7 day period is $5/7*7=5$.

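### As the SAP appendices are worded, rescue-medication incidence means any use in 7 days through Week 16 but in 28 days from Week 24 on, which contradicts SAP Section 6.2.9

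*SAP*

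**What the plan says.** The endpoint in SAP Section 6.2.9 is "Usage of rescue medication (incidence, and number of days of usage) during Weeks 1, 2, 4, 8, 12, 16, 24, 32, 40, 48, 56 and"; the list ends at Week 64. That section plans the number and percentage of subjects using rescue, on observed data and with LOCF. On the time base it says "The rescue medication data will be converted to Weekly scores for the week prior to the timepoint of interest".

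SAP Appendix 2.3 gives the derivation. Incidence is any use: "The incidence of rescue medication use will look for any incidence in the week of interest". For the meaning of a week it says "The assignment of daily and weekly data to weeks will use the same principle as described above in" Appendix 2.1, that is, as for the weekly pain score. It then states "The amount taken and number of days of rescue medication use is adjusted for the duration of the Weekly interval", which covers amount and days but not incidence.

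SAP Appendix 2.1 tabulates 7-day weeks up to Week 16 (Days 106-112). It continues: "After the Week 16 visit, these are grouped in 4-week intervals using visit windows as shown below". The Week 24 row reads "24 | 21 - 24 | 141-168". The same appendix adds further 4-week windows specifically for this endpoint, for Weeks 68 to 80, introduced by "For rescue medication, data are collected until the end of study (Week 80 or final ET").

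Protocol Section 7.1.2 has daily entries up to Week 16 and one entry per week, with past-week recall, after that.

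**The concern.** For a pain score, averaging four weekly records instead of one changes precision but hardly changes what is estimated. An any-use indicator behaves differently: a subject gets up to four chances to be positive instead of one. If the appendices are followed, the quantity labelled incidence changes between Week 16 and Week 24 while the table heading stays the same. If Section 6.2.9 is followed, it does not change. Two programmers working from the same SAP could produce different tables for Weeks 24 to 64.

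Three things are at stake: the level of rescue use reported after Week 16, the size of the arm contrast a reader takes from the percentages, and the LOCF tables, where scores made under the 7-day rule can sit beside scores made under the 28-day rule.

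**Working it through.** **The SAP's own figures first.** The Week 2 example in Appendix 2.3 (Days 8-14) has use on 5 of 7 days and 8 doses of 500 mg: 5/7 × 7 = 5 days and 8/7 × 7 × 500 = 4000 mg. The Week 9 example gives 7 days and 7/7 × 7 × 500 = 3500 mg. Both reproduce. Both are 7-day weeks before Week 16, and no example is given for a later time point.

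**Window lengths.** Last day minus first day plus 1. Week 16: 112 − 106 + 1 = 7. Week 24: 168 − 141 + 1 = 28. The Week 56 and Week 64 groups are also 28 days.

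**Effect on the level.** Inputs: weekly any-use probability p and within-subject correlation ρ between weeks. Neither is in the documents, so both are assumed and varied.

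- Independent weeks (ρ = 0): 28-day incidence = 1 − (1 − p)^4. For p = 0.20: 1 − 0.8^4 = 0.590.
- 0 < ρ < 1 (beta-binomial): with s = (1 − ρ)/ρ, a = ps and b = (1 − p)s, incidence = 1 − ∏(b + i)/(a + b + i) for i = 0 to 3. For p = 0.20 and ρ = 0.5: 1 − 0.8 × 0.9 × 0.9333 × 0.95 = 0.362.
- ρ = 1: incidence = p.

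| Weekly use | ρ = 0 | 0.2 | 0.5 | 0.8 | 1 |
|---|---|---|---|---|---|
| 20% | 59.0% | 48.4% | 36.2% | 26.1% | 20% |
| 50% | 93.8% | 85.7% | 72.7% | 59.1% | 50% |

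**Effect on arm contrasts** (differences taken before rounding).

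| Weekly, two arms | ρ | 28-day | Difference, points | Ratio |
|---|---|---|---|---|
| 20% v 10% | 0 | 59.0% v 34.4% | 10 → 24.6 | 2.00 → 1.72 |
| 20% v 10% | 0.5 | 36.2% v 19.4% | 10 → 16.7 | 2.00 → 1.86 |
| 60% v 50% | 0 | 97.4% v 93.8% | 10 → 3.7 | 1.20 → 1.04 |
| 60% v 50% | 0.5 | 81.0% v 72.7% | 10 → 8.3 | 1.20 → 1.11 |

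A small risk difference shrinks where the slope of 28-day on weekly incidence is below 1. For ρ = 0 the slope is 4(1 − p)^3, which equals 1 at p = 1 − (1/4)^(1/3) = 0.37. Numerically the turning point is about 41% for ρ = 0.2, 46% for 0.5 and 49% for 0.8. In every case tried with ρ below 1, the risk ratio moved toward 1 and the odds ratio away from 1.

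**Effect of LOCF.** SAP Section 5.3 carries the last weekly rescue score forward. The Appendix 2.3 example carries a Week 9 score, a 7-day indicator, through to Week 56. Suppose weekly use is 50% in both arms and a fraction f of an arm is carried from a 7-day score. The reported incidence is then f × 0.5 + (1 − f) × (28-day incidence).

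- ρ = 0: f = 0.5 gives 0.25 + 0.5 × 0.9375 = 0.719; f = 0.3 gives 0.15 + 0.7 × 0.9375 = 0.806. Difference 8.8 points.
- ρ = 0.5: 0.613 against 0.659. Difference 4.5 points.

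The arm with more carry-forward looks better, although weekly use is identical. The fractions 0.5 and 0.3 are assumptions. Not every subject stopped at Week 16 would bring a 7-day score: with a last dose on Day 57, the 84-day on-treatment rule for diary data in SAP Section 6.2 reaches Day 57 + 84 = 141. A subject who keeps up the diary could therefore supply a 28-day Week 20 score (Days 113-140).

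**The case against.** The strongest reply is that the 28-day rule is not settled. Section 6.2.9 says one week, the endpoint is worded by week, and the grouping sentence in Appendix 2.1 follows text about pain scores, where averaging makes sense. This stands in part: nothing shows that incidence will be programmed over 28 days. But Appendix 2.3 adopts the Appendix 2.1 rule for rescue data, and Appendix 2.1 adds 4-week windows expressly for rescue medication. The longer window is what those two appendices say when read together.

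Second, no comparison is formally at risk. Only counts and percentages are planned, SAP Section 5.1 tests no hypotheses, and in the observed-data tables all arms share the same window at each time point. This stands, and it limits the severity.

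Third, the step from Week 16 to Week 24 cannot be read as a trend under either definition. Permitted rescue use changes after Week 16 (Protocol Section 5.9), subjects failing the response criteria leave treatment (Protocol Section 6.4.5), and the diary changes from daily to weekly. This also stands. A reader might infer that any rise after Week 16 would be wholly artificial; the documents do not support that, because real use may change at the same point.

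A reader might also infer that the longer window generally compresses arm differences. It does not. With independent weeks, 40% v 20% becomes 87.0% v 59.0%: the ratio falls from 2.0 to about 1.5, but the difference widens from 20 to 28 points.

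**Conclusion.** The SAP is wrong as written on this point: Appendices 2.1 and 2.3 together give an incidence that Section 6.2.9 contradicts, and the definition changes length part-way through the series. If the appendices are followed, the definitional rise for 20% weekly use lies between 0 and 39 points, with 16 points at correlation 0.5 and 6 at 0.8. It is zero only if each subject's weekly use is constant. The direction of the effect on the risk difference depends on whether weekly use lies below or above roughly 37-49%, which the documents do not tell us. The LOCF artefact of about 9 points (independent weeks) or 4.5 points (correlation 0.5) rests on the assumed 50% v 30% carry-forward and 50% weekly use. It affects Weeks 24 to 56 only, since Section 6.2.9 does not impute after Week 56.

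This is a low-severity point on a secondary, descriptive endpoint. It does not touch the primary safety evaluation.

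**What to change.** - In Appendix 2.3, define incidence over one 7-day week at every time point: after Week 16, the weekly record for the week ending at the nominal time point (for Week 24, Days 162-168). Alternatively, report the mean of the weekly any-use indicators in the 4-week group.
- State in Appendix 2.3 that the 4-week grouping does not apply to incidence, and align the text with Section 6.2.9.
- Apply the same definition under LOCF, so that carried and observed values are on one scale.
- Footnote the table to say that permitted rescue use and the treated population also change at Week 16.

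The cost is SAP wording and one derivation. Using a single week gives slightly more missing values; the mean of the weekly indicators avoids most of that.
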